1.0 Aims

The goal of this study is to determine the extent to which standard care plus the Anticoagulation Choice tool promotes shared decision making (SDM) and impacts anticoagulation uptake and adherence versus standard care without this tool in patients with nonvalvular atrial fibrillation (AF).

Aim 1. To what extent does use of the ANTICOAGULATION CHOICE tool promote high-quality SDM versus standard care?

Using encounter video recordings and post-visit patient and clinician questionnaires, we will assess **SDM quality** (primary endpoint) **and processes**.

We hypothesize that use of the tool will improve SDM irrespective of patient literacy/numeracy, stroke risk, anticoagulation use at baseline, or type of clinic.

Aim 2. To describe the impact Anticoagulation Choice tool has on the rate of anticoagulation, the choice of anticoagulant, and adherence to anticoagulation in at-risk patients with AF versus the impact of standard care.

Using medical records and pharmacy profiles, we will determine the choice of anticoagulation, changes in anticoagulant use over time, and 12-month drug persistence, in all patients and in subgroups defined by patient literacy/numeracy, stroke risk, anticoagulation use at baseline, and type of clinic. As safety outcomes, we will monitor serious bleeding or strokes requiring medical attention.

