2.0 Background and Significance

Atrial fibrillation is the most common cardiac arrhythmia affecting ~3 million Americans^{1,2} It accounts for ~\$26 billion/year in healthcare costs.³ AF-related thromboembolic strokes are often devastating and a cause of great physical, social and economic burden.⁴⁻⁷ Vitamin K

antagonists (VKAs, e.g., warfarin) reduce the risk of stroke by ~68%.⁸⁻¹³ Recently, non-VKAs oral anticoagulants (NOACs) that directly inhibit factor Xa (e.g., rivaroxaban, apixaban, edoxaban) or thrombin (dabigatran) have demonstrated similar to or better efficacy and safety than warfarin.¹⁴⁻¹⁶ Underuse of anticoagulation is a significant quality gap. Despite patients' strong aversion to strokes,^{17,18} <50% of high-risk patients with AF receive anticoagulants.¹⁹ Of these, 30-50% stop treatment within 12 months.²⁰⁻²³ The low rate of anticoagulation suggests that clinicians are challenged in initiating anticoagulation, in part due to clinicians' aversion to causing anticoagulation-related bleeding,^{19,24} Nonadherence suggests that some patients cannot implement anticoagulation in their lives: warfarin requires a stable diet and periodic laboratory (INR) monitoring,²⁵⁻²⁷ while NOACs are costly and lack bleeding reversal agents.¹⁴⁻¹⁶ Underuse may result also from poor patient and clinician access to, and deliberation with, individualized estimates of risks and benefits.^{28,29} Patients and clinicians require support in initiating and implementing anticoagulation therapy.

In 2014, three major cardiovascular organizations formulated guidelines for the management of patients with AF. They gave their strongest class I recommendation for using SDM to individualize anticoagulation in at-risk AF patients.³⁰ SDM has the potential to support patients and clinicians in collaborative deliberation about reasonable anticoagulation strategies matched to medical risk and patient circumstance.³⁰⁻³² Nevertheless, this recommendation is based on expert consensus (level C evidence) and translating it into practice is challenging. The guideline provides no guidance on how to achieve this, and no tools were available that are both up-to-date and proven to support SDM in this context. Furthermore, we do not know what effect SDM may have on anticoagulation rates and adherence in patients with AF.³⁰

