Data to be collected on patients include variables necessary to estimate the risk of stroke and bleeding, age, gender, BMI, smoking status, alcohol consumption, marital status, annual income of household, highest level of education, residency (nursing home), location of primary healthcare and total number of medications patients is currently taking. To further characterize the patients, we will use Chew et al single-item health literacy screener,⁴⁶ a 4-item modified Subjective Numeracy Scale,^{47, 48} and a single-item health status measure.⁴⁹

We will collect information on past use of anticoagulants through medical record review. We will categorize the patients into two cohorts for descriptive and analytical purposes. For patients who are not using an anticoagulant at the time of trial participation will form the 'Start' cohort. They may have used anticoagulation and discontinued >6 months ago, never used anticoagulation, or are using aspirin only. Patients that began an anticoagulant

within the past 10 days of the enrolled encounter that were prescribed an anticoagulant within the emergency department or an inpatient visit will still be considered a new ‘Start’.

Patients who are on warfarin or NOACs or used them in the past 6 months will form the ‘Review’ cohort. This cohort may include patients who have difficulty maintaining a therapeutic INR, or patients considering switching to a different anticoagulant or to stay on warfarin but switch to home INR monitoring.

The post consent survey for clinicians will collect demographic data (age, gender, specialty, % of their practice dedicated to anticoagulation care).

Calendar of Events

	Prior to Study Enrollment	Prior to Encounter		Post Encounter	12 months Post Enrollment
Patient Completed Forms			R A N D O M I Z E D A T I O N		
Informed Consent	X				
Pharmacy Consent	X				
Survey				X	
Phone ¹					X
Clinician Completed Forms					
Informed Consent	X				
Survey		X		X	
Clinical Data Abstracted from EMR					
Bleeds					X
Strokes					X
INR Tests (# and values outside of 2-3 range)					X
Anticoagulation Prescription		X		X	X
Pharmacist Request					
Anticoagulation					X ²

Use					
-----	--	--	--	--	--

- 1- Patients who do not have utilization within enrolling healthcare system will be contacted via phone for verification of safety data (strokes and bleeds). If no information in the record and follow-up is necessary we will call patients the maximum number allowed by the IRB followed by a postal survey

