- 2- Pharmacist records will be requested for 12 months prior to enrollment through 10 months post enrollment.

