4.7.3 Anticoagulation Use

Rate of anticoagulation: The key indicator of the choice to start an anticoagulant will be its prescription in the EMR prescription module (observed discussions and patient/clinician accounts may not reflect decisions confirmed after the visit with a prescription, for example, after the clinician or the patient checked other information or with other informants). After this primary ‘decided as prescribed’ approach, we will conduct secondary analyses using patient/clinician reported and video-observed decisions. Decisions may be for starting or not an anticoagulant in the start cohort. It is possible that there may be some decisions to stop anticoagulation in the review cohort, but we expect start and review cohorts to contribute information about choice of anticoagulant.

Choice of anticoagulant: We will review the EMR and 10-month pharmacy profiles (to stand for the 12-month profile given the automatic expiration of pharmacy records at 1 year) to determine the prescribed anticoagulant and whether and when switches to another agent or to no anticoagulant took place.

Together, they should capture choice and switches even when these occur as a result of changes in clinician (e.g., from cardiology to primary care). When available, we will note the documented reasons from clinical notes for choosing and switching as well as with which clinician the change was made (e.g primary, cardiology, etc.).

Anticoagulation persistence: Patients will identify the pharmacy(-ies) they use to fill their prescriptions and authorize us to obtain their prescription drug fill data. We will calculate anticoagulation persistence, using the percent days covered (PDC) based on prescription refill behaviors (total days supply of anticoagulant filled / total days of observation from the first prescription fill date; range 0-100%). We will also pull all pharmacy refills for the 12 months prior to enrollment. This will allow us to calculate persistence for prior use of anticoagulants for the review cohort to compare to persistence post encounter and see if there is an impact.

Warfarin use: For patients who choose to stay on warfarin, we will also use as secondary measures of adherence: (a) the proportion of INR tests obtained/scheduled; and (b) percentage of time at therapeutic target (typically INR 2-3).

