4.9 Statistical Analysis

4.9.1 Analysis Plan

The study will be analyzed according to the *intention to treat principle (ITT)*, including all patients enrolled to the study in the arm to which they were assigned, regardless of which they were assigned to (e.g., standard care or Anticoagulation Choice + Standard Care). Reporting will include 'Per Protocol', complete data for each arm plus the ITT analysis where imputation analysis methods will be utilized to address any missing values (see section 4.9.1.1 for details on missing data analysis). Baseline characteristics will be reported in the study results with continuous values being reported as means and standard deviations and categorical values reported as counts and frequencies and compared between study arms using t-tests and chi-squared tests. Any baseline imbalances ($p < 0.05$) will be explored as a possible factor to adjust for when the outcome measures are

analyzed. We will adhere to the CONSORT guidelines to transparently report study results and ensure that sufficient information is included to allow for assessment of the study's internal and external validity.

We will use standard techniques appropriate for trials, with each outcome compared between study arms using t-tests for continuous outcomes and chi-square tests for dichotomous outcomes. If there are differences in baseline characteristics found by statistical means or found to have clinical relevance between the two study groups, these will be accounted for using regression models which include an indicator for study arm.

We will perform descriptive analyses to describe any potential heterogeneity of treatment effect (HTE) and facilitate synthesis of subgroup results in future meta-analyses. We will conduct descriptive HTE analyses by clinic (academic, community and safety net), by cohort (start or review cohort), by stroke risk (CHA₂DS₂-VASc score of 1 or ≥ 2 for men and 2 or ≥ 3 for women), and by numeracy (Less than adequate vs. not). The outcomes assessed with HTE analyses will be the same as those assessed in the trial (e.g., SDM and communication quality, knowledge, and decisional satisfaction).

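### The before/after persistence comparison in the review cohort is to be read as impact without being tied to the randomised arms

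*Combined protocol and SAP*

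**What the plan says.** Section 4.7.3 defines persistence as the percentage of days covered (PDC), counted from the first fill. It then adds that fills from the year before enrolment will be used to "calculate persistence for prior use of anticoagulants for the review cohort to compare to persistence post encounter and see if there is an impact". It does not mention study arm, a test, or whether the comparison is paired within patient.

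Three other places bear on how such a change behaves:

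- Section 4.6 defines the cohort by use: "Patients who are on warfarin or NOACs or used them in the past 6 months will form the" review cohort.
- The notes to the calendar in Section 4.6 set the periods: "Pharmacist records will be requested for 12 months prior to enrollment through 10 months post enrollment".
- Section 2.0, on high-risk patients who receive anticoagulants: "Of these, 30-50% stop treatment within 12 months".

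The general plan is between arms. Aim 2 concerns "adherence to anticoagulation in at-risk patients with AF versus the impact of standard care" and looks at 12-month persistence "in all patients and in subgroups defined by patient literacy/numeracy, stroke risk, anticoagulation use at baseline, and type of clinic". Section 4.9.1 has "each outcome compared between study arms using t-tests for continuous outcomes and chi-square tests for dichotomous outcomes". Section 4.9.2 powers persistence as usual care against the tool arm, and Section 4.9.3 stratifies randomisation by start or review cohort.

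**The concern.** The periods before and after the encounter are not exchangeable, even if the tool does nothing.

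- **Selection on use.** A patient enters the review cohort by using an anticoagulant now or within 6 months. The earlier period is conditioned on use and the later one is not, so ordinary stopping pulls the later value down among current users.
- **Recent stoppers.** The cohort also includes patients who stopped within 6 months. If they restart for any reason, the later value rises.
- **Unequal periods.** The look-back is 12 months and the follow-up 10.

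An analyst who follows the sentence literally could report an uncontrolled change as an effect of the tool, or report a fall as harm. If the change is taken over the whole review cohort, as the wording allows, it also includes the control patients, for whom the tool was not to be used.

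**Working it through.** **Records available.** Section 4.9.2 expects about 765 persistence records: 999 × 0.90 × 0.85 = 764, which reproduces it. With the even start/review split assumed there, the review cohort has about 382 records, or 191 per arm if allocation is 1:1 (the ratio is not stated).

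**The plan's power figure.** Section 4.9.2 gives 80% power for 60% versus 69%. With 382 per arm, SE = √[(0.60×0.40 + 0.69×0.31)/382] = 0.0345, and Φ(0.09/0.0345 − 1.96) = 74% (74.0% with pooled variance). That gap is a separate matter. What counts here is that the calculation is between arms.

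**Direction is not fixed.** A current user with full prior coverage can only stay level or fall. Now take a patient who filled for the first 7 of the 12 prior months, stopped 5 months ago and restarts at the visit. Prior PDC is 7/12 = 58%, and later PDC can reach 100%. The sign of the average change depends on the mix of such patients, which the documents do not give.

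**The look-back length matters.** For that same patient, the last 10 months hold 5 covered months: 5/10 = 50%, against 58% over 12 (assuming a fill at the start of each window). How much this shifts the cohort average cannot be derived from the documents.

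**Effect of drift on the error rate.** Assumptions: no tool effect; PDC continuous and normal, SD 30 points, mean 70% before; pre/post correlation r of 0.3, 0.5 or 0.7; the same natural fall in both arms; 191 per arm; 2,000 simulated trials per setting; two-sided 5% tests. The table gives the percentage of trials that are significant.

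| Natural fall | Before/after test in the tool arm (r = 0.3 / 0.5 / 0.7) | Change compared between arms (range over r) |
|---|---|---|
| 0 points | 5 / 5 / 6 | 5.1-5.6 |
| 3 points | 21 / 27 / 42 | 4.4-4.8 |
| 5 points | 48 / 63 / 84 | 4.9-6.0 |
| 10 points | 97 / 99 / 100 | 4.7-5.7 |

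Hand check for r = 0.5 and a 5-point fall: SD of change = 30 × √[2(1 − 0.5)] = 30; SE = 30/√191 = 2.17; 5/2.17 = 2.30; Φ(2.30 − 1.97) ≈ 63%, which agrees. A natural rise of the same size would act the same way.

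**Value of prior PDC as a covariate.** Residual variance falls by about r². For an assumed r of 0.3 to 0.6 that is 9% to 36%, if prior PDC is known for everyone.

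**The case against.** A reader might infer that the tool's effect in the review cohort is to be judged by the before/after comparison. The documents do not support that. The sentence sits under outcome measures and describes additional data. The analysis rules are in Section 4.9.1 and are between arms, Aim 2 is set against standard care, and the power statement is between arms. Other outcome descriptions in Section 4.7.3 name no arm either. The sentence is compatible with comparing the change by arm, in which case the drift cancels. Pairing within patient is also an inference.

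A reader might also turn the 30-50% stopping figure into a specific expected fall in coverage. That would need full coverage before enrolment, which conflicts with a cohort that admits recent stoppers, and it would apply a rate quoted for treated patients generally to established users.

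Persistence is not the primary endpoint, and Aim 2 is worded as descriptive. Not adjusting for prior PDC is a choice about precision, not an error.

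All of this limits the point without removing it. Section 4.9.1 governs outcomes, but does not say that the before/after change is one or that it will be contrasted by arm. Its regression adjustment is triggered by baseline differences found between the groups, so prior PDC is not a prespecified covariate. In Section 4.7.2, by contrast, the fidelity score is explicitly compared between arms.

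**Conclusion.** The point holds in limited form. One added analysis is described as showing impact without being linked to the arms; the main persistence comparison is not affected. Read literally, the change confounds the tool with discontinuation, restarts and unequal periods.

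The documents fix neither the size nor the direction of the bias. The simulated error rates (21-42% for a 3-point fall, 48-84% for 5 points, 97-100% for 10) rest on assumed drift, SD, correlation, allocation ratio and an even cohort split. They show that modest drift is enough to mislead and are not a forecast. The between-arm contrast stayed at 4-6% in every setting. This should be corrected, and wording is enough.

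**What to change.** Replace the sentence in Section 4.7.3 with:

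> In the review cohort, the effect on persistence is the between-arm difference in post-encounter PDC, from a regression with arm and prior PDC as covariates, with prior PDC calculated over the 10 months before the encounter. Within-arm before/after changes are descriptive only.

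Add that patients with missing prior PDC stay in the analysis, by baseline imputation or a missing-value indicator. It would also help to say how patients with no fill after the encounter are scored, because a PDC counted from the first fill is undefined for them.

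The change uses fills the plan already requests and a stratum it already randomises by. The cost is the wording, two prior months left unused, and the handling of missing prior values. Those may be common: Section 4.7.3 notes that pharmacy records expire at 1 year, and the calendar places the pharmacist request at 12 months after enrolment. The gain in precision may therefore be smaller than the illustrative 9-36%.

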4.2.3 Identification of Subjects

Participants for all aims will be patients, their caregivers when pertinent, and clinicians. Participation is completely voluntary and we have procedures in place, sanctioned by the Mayo Clinic Institutional Review Board, Hennepin County Medical Center Institutional Review Board (HCMC), Park Nicollet Health Partners Institutional Review Board, UAB Medicine - The University of Alabama at Birmingham Institutional Review Board and University of Mississippi Medical Center Institutional Review Board to ensure that participants have the opportunity to opt out at any time and will not be further approached for participation or to provide data.

At the Mayo Clinic site, upcoming appointment lists for Atrial Fibrillation (AF) patients in primary care, cardiology, neurology, thrombophilia and anticoagulation clinics ECG result lists, medical records and clinician referrals will be reviewed for patient eligibility. Eligible patients will be approached and recruited in person, in a private location (i.e., clinic/exam room) prior to their appointment. Consent will occur by a trained research member as long as needed and until all questions by the subject have been answered. All study activities will occur within scheduled appointments, avoiding the need for additional research visits.

The patient and caregivers (if present), will be asked to provide consent to the recording (video/audio or audio only) of the clinical encounter. If the patient chooses to decline the recording they are still eligible to participate in the study. The study coordinator will quickly setup and start recording before leaving the room. The participants can stop this

recording (video, aimed at the desk, or audio when the video camera is aimed at the ceiling) at any time (the device has a large red start/stop button and an on/off indicator light).

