4.3 Registration and Randomization of Patients

Prior to registering patients to the study, all of the eligibility criteria on the eligibility checklist will have been met.

Patients will be randomized by the study coordinator after completion of standard informed consent for participation in clinical research including permission to use protected health information.

Registration/randomization is available via REDCap

 this is a secure, web-based application that is HIPPA compliant. Registration/randomization is available 24 hours a day via the REDCap website. Site staff will be provided a login and password by the study statistician.

Prior to accessing the REDCap website, site staff should verify the following:

- All eligibility criteria have been met.
- Informed consent has been obtained.
- Site staff has access to REDCap.

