4.5 Standard Care

The clinician will conduct the encounter per their standard of care. As access to the tool will be available to ensure contamination does not occur the study coordinator will inform the clinician prior to entering the room that the patient is to receive standard care and that the tool is not to be accessed.

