4.6 Data Collection

Patients approached by study staff that agrees to participation will be captured in the remote data capture system (REDCap⁴⁵). Potential eligible patients found to be ineligible or eligible but decline participation will be captured in a recruitment tracking log. The reason for ineligibility or reason for decline will be captured along with patients' age, sex, and race/ethnicity.

Self-reported responses from patients and clinicians will be collected at the end of the clinical encounter. At the time of their enrollment clinicians will complete a survey that collects data on their demographics. The post baseline survey will be given to the patient and clinician to complete at the clinic at the end of the encounter by the study coordinator or site appointed staff. Patients may be given the option to fill out part of the survey, prior to their visit if time allows. If a patient requests a return envelope, one will be provided to return the survey by mail. If the survey is not received in the 10 days post encounter a

reminder will be mailed to them with a copy of the survey along with a return envelope. A courtesy call will be made within 5 days post the mailing. Every effort will be made to complete the survey at the clinic immediately post encounter as this is the best chance for complete data collection. Another option for patients will be to have a follow up phone call approximately 1-2 days after their clinical encounter, to remind the patient to send their survey back or they will be given the option to complete their survey over the phone at that time.

Data from the medical record will be abstracted for all enrolled patients to capture demographic, clinical and medication prescription data. The time frame for collection will be from prior to enrollment to 12 months post enrollment. For patients that do not have any encounters at the institution for the past 12 months, a scan will be conducted up to 6 months after the 12-month timeline to verify continuity of care at the institution, change in contact information and/or survival status. If no records are available at that time, we will call the patient (number of attempts as authorized by each IRB), followed by a postal survey if nonresponse persist.

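### The INR items listed for abstraction do not determine either warfarin adherence measure, and both measures apply to a subset formed after randomisation

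*Combined protocol and SAP*

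**What the plan says.** Section 4.7.3 introduces the warfarin measures with "For patients who choose to stay on warfarin, we will also use as secondary measures of adherence" and defines them as "a) the proportion of INR tests obtained/scheduled; and (b) percentage of time at therapeutic target", with 2-3 given as the typical INR target. It gives no method for calculating either.

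The only statement of which INR data are collected is a row in the Calendar of Events in Section 4.6, under data abstracted from the medical record at 12 months: "INR Tests (# and values outside of 2-3 range". The general text of that section, "Data from the medical record will be abstracted for all enrolled patients to capture demographic, clinical and medication prescription data", adds no INR item.

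On timing, Section 4.3 says "Patients will be randomized by the study coordinator after completion of standard informed consent". Section 4.2.3, in its text for the Mayo Clinic site, says "Eligible patients will be approached and recruited in person, in a private location (i.e., clinic/exam room) prior to their appointment". Section 4.5 says that in the control arm "the study coordinator will inform the clinician prior to entering the room that the patient is to receive standard care". The calendar places randomisation between its pre-encounter and post-encounter columns.

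Section 1.0 (Aim 2) and Section 4.7.3 treat choice of anticoagulant as an outcome. Section 4.9.1 plans to compare each outcome between arms by t-test or chi-square test, and it does not exempt the INR measures.

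**The concern.** There are two linked problems.

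- **Data capture.** Time at target depends on when each test was done and on its value, including the values inside the range. The ratio of tests obtained to tests scheduled needs a count of scheduled tests. The calendar row lists none of these. It also fixes the range at 2-3, whereas Section 4.7.3 calls that range only typical. If abstraction follows the calendar, what can be computed is the proportion of tests in range, which is a different quantity from the one named.
- **Population.** The measures are defined among patients who remain on warfarin. That decision is taken in or after an encounter whose allocation is already fixed, and the tool is meant to inform it. Section 4.6 says that the review cohort may include patients whose INR is hard to keep in range and patients thinking of switching, so INR control may be related to who stays. A between-arm difference in this subset could arise without any effect on adherence.

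At stake is whether two stated secondary measures can be reported as named, and whether a difference in them could be misread as an effect of the tool.

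**Working it through.** The plan gives no expected value, sample size or power for the INR measures, so there is no figure to reproduce. The check asks whether the listed data determine the measures. All numerical inputs below are assumptions chosen for illustration.

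**1. Time in range.** Method: linear interpolation of INR between consecutive tests, with range 2-3. Take six tests, two at 1.5 and four at 2.5. The calendar would record six tests and two out-of-range values of 1.5. Share of tests in range = 4/6 = 66.7%.

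An interval from 2.5 to 2.5 is wholly in range (1). An interval from 1.5 to 1.5 is wholly out (0). An interval between 1.5 and 2.5 crosses 2.0 at its midpoint (0.5). With equal spacing there are five equal intervals:

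- Order 2.5, 2.5, 1.5, 1.5, 2.5, 2.5: (1 + 0.5 + 0 + 0.5 + 1)/5 = 3/5 = 60%.
- Order 1.5, 2.5, 2.5, 2.5, 2.5, 1.5: (0.5 + 1 + 1 + 1 + 0.5)/5 = 4/5 = 80%.

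The listed data are the same in both, and the results lie on either side of 66.7%.

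Keep the first order and change only the dates:

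- Days 0, 150, 165, 172, 187, 330: (150 + 7.5 + 0 + 7.5 + 143)/330 = 308/330 = 93.3%.
- Days 0, 15, 30, 300, 315, 330: (15 + 7.5 + 0 + 7.5 + 15)/330 = 45/330 = 13.6%.

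Keep the first order and equal spacing, and change only the unrecorded in-range values:

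- All four at 2.0: (1 + 0 + 0 + 0 + 1)/5 = 40%.
- All four at 3.0: (1 + 2/3 + 0 + 2/3 + 1)/5 = 66.7%.

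The date example is deliberately extreme. It shows that time in range is not identified; it does not predict the size of the error in this trial.

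**2. Tests obtained over tests scheduled.** Suppose 10 tests were obtained. The ratio is 10/10 = 100%, 10/12 = 83%, 10/15 = 67% or 10/20 = 50%, depending on an unlisted denominator (assumed range 10 to 20).

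**3. Selection into the subset.** Assume that half of warfarin users have 75% time in range and half have 45%, and that the tool has no effect on control.

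- Control arm, 80% of each group stay: (0.8 × 75 + 0.8 × 45)/1.6 = 60.0%.
- Tool arm, 80% of the well controlled and 60% of the poorly controlled stay: (0.8 × 75 + 0.6 × 45)/1.4 = 87/1.4 = 62.1%.
- Tool arm, 80% and 40% stay: (0.8 × 75 + 0.4 × 45)/1.2 = 78/1.2 = 65.0%.

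The apparent difference is 2.1 to 5.0 points, produced only by who stayed.

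**The case against.** The calendar is a summary grid and not a data dictionary. Neighbouring rows are equally terse: the pharmacy row does not list fill dates or days of supply, although the persistence measure in Section 4.7.3 plainly uses them. INR results in a medical record normally carry dates, and the case report form is not among the documents. A reader might infer that the two measures can never be produced in this trial. The documents do not support that. They support only that the items as listed are insufficient and that no other text supplies the rest. That part of the objection stands, but the row does name specific items, and those items give only the share of tests in range.

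A reader might also infer that the share of tests in range understates time in range, on the view that out-of-range results are retested sooner. The documents give no retest intervals, and step 1 shows the discrepancy going either way.

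On selection, INR measures have meaning only in warfarin users, Aim 2 is worded as descriptive, and no power or causal claim is attached to these measures. This limits the weight of the point. However, Aim 2 also sets the tool against standard care, and the general testing rule in Section 4.9.1 covers every outcome. That section also promises imputation of missing values without saying whether a patient who leaves warfarin has a missing value or none to measure.

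**Conclusion.** The point holds as a mismatch between the calendar in Section 4.6 and the definitions in Section 4.7.3, together with an unaddressed post-randomisation subset. As listed, the data leave time in range undetermined: 60% or 80% from test order alone at 66.7% of tests in range. They also leave the ratio of tests obtained to tests scheduled without a denominator. The example rests on the assumed INR values and spacing and on linear interpolation.

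The selection effect is possible, not demonstrated. The 2.1 to 5.0 points rest on assumed staying rates. The documents give neither switching rates by arm nor the number of warfarin users, so it would be wrong to infer that a difference in these measures must be biased. The subset, read literally, is existing users who continue; it should not be read as everyone who picks warfarin after randomisation, since new starters appear to be left out.

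The matter is minor. These are secondary measures, additional to pharmacy-based persistence, and the primary SDM endpoint is unaffected.

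**What to change.** - **Calendar of Events, Section 4.6.** Replace the INR row with every INR value and its date, the patient's recorded INR target and, where retrievable, each scheduled INR test, over the 12 months in warfarin users.
- **Section 4.7.3.** State that time at target is computed by linear interpolation between dated values against the recorded target.
- **Fallback.** If dates cannot be obtained, rename measure (b) as share of INR tests in range. If schedules cannot be obtained, drop measure (a).
- **Section 4.9.1.** State that these measures are reported descriptively by arm, with the number of patients contributing, and without a between-arm test or a claim of effect.

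The cost is modest extra abstraction for warfarin users, largely from records already being opened. Scheduled tests may be the hard part, because Section 4.6 mentions home INR monitoring and Section 4.2.3 mentions records held at outside clinics; hence the fallback. Settling this before abstraction starts avoids reopening charts.
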